The study population for this project will include neonates and infants (less than 1-year-old) who are undergoing repair of aortic coarctation via thoracotomy with no other simultaneous surgical procedure. The patients will undergo a standardized anesthetic. Patients in the experimental arm will receive a paravertebral nerve block for intraoperative and postoperative pain control supplemented with narcotic as needed while the control arm will receive standard of care, which will include additional narcotic as indicated and local anesthetic infiltrated into the wound after the procedure. Each group will have their spinal cord regional saturations measured with NIRS. Regional anesthetic techniques in children are relatively low risk endeavors and the primary concern is risk of regional block failure. More significant, but very rare complications could include local anesthetic systemic toxicity (LAST), tissue hematoma (bleeding), epidural hematoma (bleeding), unintentional epidural spread, and prolonged sensory blockade. [5]

The primary aim of this study is to determine the feasibility of studying whether a single-shot paravertebral nerve block is effective in providing intraoperative and postoperative pain control in infants undergoing a thoracotomy for coarctation of the aorta. This will be determined by comparing morphine equivalent consumption in the standard of care and intervention groups. Secondary outcomes include plasma epinephrine levels (three times per patient) to determine stress hormone response in both groups, NIRS values to monitor the difference in spinal cord oxygen supply between the intervention and control group, time to first feeding (another measure of pain control in this age group), and total ventilator time.

The following aims are proposed:

Primary Aim

1. Determine the feasibility of studying whether total narcotic administration is less in subjects who receive the peripheral nerve block versus standard of care.

Hypothesis: Patients undergoing the experimental technique, paravertebral nerve block, will have less pain and therefore will consume fewer morphine equivalents in the 48-hour post-op follow-up period. This difference will be measurable and provide sample size estimations for future studies.

Evaluation Method: All narcotics used in the 48-hour post-op period will be tabulated and converted to morphine equivalents. Other non-narcotic analgesics will also be tabulated, but can't be converted to morphine equivalents.

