Secondary Aims

2. Measure whether spinal cord perfusion can be improved during aortic cross clamp by improving collateral blood flow with regional anesthesia techniques.

Hypothesis: Near infrared spectroscopy (NIRS) values will decrease in the control and study group during aortic cross clamp but values in the study group will be 41% higher than control due to increased collateral blood flow.

Evaluation Method: Continuous measurement of spinal cord NIRS values during repair of aortic coarctation, including the aortic cross clamp period.

3. Determine the total time required for post-op ventilation in each group.

Hypothesis: Post-op ventilation times will be lower in those patients undergoing the experimental technique, paravertebral nerve block, because these patients will have less respiratory splinting from better analgesia and be less sedated from less sedative and analgesic use.

Evaluation Method: Time until extubation.

4. Determine the time to first feeding in each group.

Hypothesis: Patients who undergo the experimental technique, paravertebral nerve block, will have earlier return to feeding since they will have better analgesia and less sedation from narcotics.

Evaluation Method: Time until first feeding.

5. Measure stress response to surgery in the experimental and control groups.

Hypothesis: Patients who undergo the experimental technique, paravertebral nerve block, will have better suppression of the natural stress response to surgery.

Evaluation Method: Plasma epinephrine levels measured at baseline (before incision), postoperatively (just before transfer to the Intensive Care Unit), and 24 hours postoperatively.

Introduction, Background, and Significance to Our Mission

Repair of aortic coarctation is a commonly performed operation. The repair is performed via thoracotomy which is a surgical incision that is commonly complicated by atelectasis, desaturation, and pain in the adult population. To prevent these complications, it has been shown that regional or neuraxial anesthesia can decrease the amount of pain the patient has, which allows for deeper breathing and fewer desaturations from atelectasis. We propose, in this study, to examine the benefits of paravertebral peripheral nerve block in the neonatal and infant populations. Regional anesthesia has the potential to decrease narcotic requirements in children undergoing painful operations, decrease ventilator time, and manipulate the stress response to surgery. [1] [2] [3]

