Pain remains a significant concern in the neonatal and infant populations. There is evidence that pain is often undertreated in order to accomplish other goals of medical management including earlier extubation. Furthermore, pain control with narcotic medications are an additional concern and withdrawal from narcotics can become an issue in those neonates and infants requiring long-term administration of these medications. Therefore, further study into alternative methods of pain control are warranted.

Significance:

Specific Aim #1:

Use of paravertebral nerve block in these patients may improve pain control for these patients and decrease the total burden of narcotic administered.

Specific Aim #2:

Use of regional anesthesia to encourage collateral blood flow may be spinal cord protective as evidenced by an improvement in the NIRS during aortic cross clamp in the experimental group.

Specific Aim #3:

Decreased time to extubation may be made possible in the experimental group, which would help to prevent ventilator associated complications including barotrauma, pneumothorax, pneumomediastinum and ventilator associated pneumonia.

Specific Aim #4:

Decreased time to first feeding may be facilitated by earlier extubation and less sedation in the experimental group.

Specific Aim #5:

Decreased stress response to surgery is generally associated with fewer physiologic perturbations and may be facilitated by the use of regional anesthesia compared to the standard of care group.

Experimental Design and Methods

Design:

This study is designed to be a prospective, randomized, non-blinded clinical trial. After informed and written parental consent, a total of 30 neonates and infants (<1 year old) will be enrolled. Subjects will be assigned to nerve block or SOC in a 1:1 ratio. Random treatment assignment

will be accomplished using a permuted block design with random block sizes of 2 or 4. Randomization will be done by study statistician using SAS v. 9.4 (Cary, NC).

Study Population:

A total of 30 neonates and infants, defined as children less than 12 months of age, will be enrolled in this study. The subjects will be scheduled for elective or semi-elective cardiac surgery at Children's Healthcare of Atlanta.

The following criteria will be used to determine patient eligibility:

Inclusion Criteria:

- Neonate or Infant (<12 months age) at the time of surgery
- ≥ 2.5 kg at the time of surgery
- Undergoing aortic coarctation repair via left thoracotomy

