Participants in the control arm will undergo an anesthetic consistent with the standard of care. The patient will be induced for anesthesia with propofol 3mg/kg or ketamine 2mg/kg (if there is intravenous access) or sevoflurane with 1 mcg/kg of fentanyl and 1.2 mg/kg rocuronium once IV access is established. The patient will be intubated; intravenous and intra-arterial access will be obtained and the patient will be positioned for surgery. A NIRS pad will be used for cerebral oximetry as well as another NIRS pad for spinal cord oximetry. Fentanyl may be used as needed for additional analgesia and anesthesia will be maintained with sevoflurane. The skin will be infiltrated at the conclusion of surgery with less than 1 mL/kg of 0.25% bupivacaine with epinephrine 1:200k. The patient will be returned to the ICU intubated unless the anesthesia provider considers them to be an excellent candidate for early extubation. Every patient will have an epinephrine level drawn pre-incision in the operating room, post-operatively upon arrival to the intensive care unit, and 24-hours post-operatively (unless there is no existing vascular access that allows the level to be drawn 24-hours post-operatively). The 24-hour post-operative time point will be defined as 24-hours after arrival to the CICU.

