Participants in the experimental arm will undergo an anesthetic that includes the regional anesthetic technique, paravertebral nerve block. The patient will be induced for anesthesia with propofol 3mg/kg or ketamine 2mg/kg (if there is intravenous access) or sevoflurane with 1 mcg/kg of fentanyl and 1.2 mg/kg rocuronium once IV access is established. A NIRS pad will be used for cerebral oximetry as well as another NIRS pad for spinal cord oximetry. The patient will be intubated, and then will be positioned laterally for the nerve block at approximately the left T3-4 level. A 13-6 MHz, linear ultrasound probe with a sterile sheath will be used to provide imaging for the paravertebral nerve block. A Pajunk SonoPlex 50mm, 22 gauge, facet tip needle will be used. The injected solution will be 1 mL/kg of 0.2% ropivacaine with 5 mcg/mL (1:200k) epinephrine. Ropivacaine is a standard drug used in this patient population for regional nerve blocks and is non-experimental as part of this protocol. The paravertebral block needle insertion site and sterile field will be observed and the block will be performed or supervised by one of the study investigators. Fentanyl may be used as needed for additional analgesia and anesthesia will be maintained with sevoflurane. The skin will not be infiltrated with additional local anesthetic at the conclusion of the case. Every patient will have an epinephrine level drawn pre-incision in the operating room, post-operatively upon arrival to the intensive care unit, and 24-hours post-operatively (unless there is no existing vascular access that allows the level to be drawn 24-hours post-operatively). The 24-hour post-operative time point will be defined as 24-hours after arrival to the CICU.

Post-operative pain control in either the control or experimental (paravertebral nerve block) group will be accomplished with intravenous, rectal, and oral analgesics. Patients will receive scheduled rectal acetaminophen while intubated and oral acetaminophen once they have progressed to oral intake of formula. Intravenous fentanyl or morphine will be used for

breakthrough pain while intubated and until oral intake is tolerated. Once oral intake is resumed, the patient will be provided with oral oxycodone as needed for pain and additional doses of IV morphine as needed for severe pain.. If the patient is not yet ready for extubation and requires additional sedation, intravenous doses of midazolam may be required.

Sample Size/Statistics

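### Aim 5's immediate post-op epinephrine contrast mixes injected with endogenous epinephrine, because both arms receive epinephrine on different schedules; the post-op draw also has two contradictory times

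*Combined protocol and SAP*

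**What the plan says.** The Abstract gives the purpose of the measurement: "Secondary outcomes include plasma epinephrine levels (three times per patient) to determine stress hormone response in both groups". No other Aim 5 measure is named. The Aim 5 hypothesis is that block patients "will have better suppression of the natural stress response to surgery".

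The injections are described in Study Description:

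- **Control arm:** "The skin will be infiltrated at the conclusion of surgery with less than 1 mL/kg of 0.25% bupivacaine with epinephrine 1:200k".
- **Block arm:** "The injected solution will be 1 mL/kg of 0.2% ropivacaine with 5 mcg/mL (1:200k) epinephrine". This is described after intubation and lateral positioning. The same paragraph rules out local anesthetic infiltration of the skin at the end of the case.

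The post-op draw has two times. Aim 5 (Evaluation Method) says: "Plasma epinephrine levels measured at baseline (before incision), postoperatively (just before transfer to the Intensive Care Unit), and 24 hours postoperatively". Study Description, in identical words for each arm, calls for "an epinephrine level drawn pre-incision in the operating room, post-operatively upon arrival to the intensive care unit". For the last sample, "The 24-hour post-operative time point will be defined as 24-hours after arrival to the CICU", and it is skipped if no vascular access remains.

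Sample Size/Statistics compares secondary outcomes between arms with t-tests or Wilcoxon tests and asks for effect sizes with 95% confidence intervals. It intends those effect sizes to inform a larger trial. The plan does not treat injected epinephrine as a source of the measured level, ask for injection or draw times to be recorded, or order the block relative to the baseline draw.

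**The concern.** The substance assayed is also a substance injected, on a schedule set by the assigned arm. Randomisation, intention-to-treat analysis and a larger sample do not remove such a difference, because it is part of the treatment comparison. Any injected epinephrine still in plasma at the post-op draw would be counted as stress response.

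The two sources pull in opposite directions. A residue from the control infiltration would raise control levels and imitate the hypothesised suppression by the block. A residue from the block would raise block-arm levels and hide it. Since pilot effect sizes are meant to feed later planning, an error in either direction matters.

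The conflicting draw times are a separate problem: one of the three samples has no single definition.

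**Working it through.** **1. The plan's own figure.** A 1:200k solution contains 1,000,000 mcg / 200,000 mL = 5 mcg/mL, which matches the concentration stated for the block.

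**2. Injected load** (volume per kg × 5 mcg/mL; the minimum weight in Inclusion Criteria is "2.5 kg at the time of surgery").

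| Arm | Volume | Load | At 2.5 kg |
|---|---|---|---|
| Block | 1 mL/kg | 1 × 5 = 5 mcg/kg | 12.5 mcg |
| Control | under 1 mL/kg, no minimum | under 5 mcg/kg | under 12.5 mcg |

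At assumed control volumes of 0.25, 0.5 and 0.75 mL/kg the load would be 1.25, 2.5 and 3.75 mcg/kg.

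**3. Sequence.**

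| Step | Block arm | Control arm |
|---|---|---|
| Before incision | baseline draw and block, order not stated | baseline draw |
| End of surgery | no infiltration | epinephrine-containing infiltration |
| Post-op draw: before transfer (Aim 5) or on ICU arrival (Study Description) | after the block | after the infiltration |
| 24 h after CICU arrival | no planned arm-specific epinephrine injection shortly before | same |

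Under either post-op time, each arm has already had its injection, and the intervals from injection to draw differ by design. The documents give no absorption, clearance, infiltration-to-draw interval or SD, so the effect on the plasma level cannot be computed.

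**4. Illustration under assumed shifts.** Let c be the rise in controls from the infiltration and b the residue from the block, both in SDs at the post-op draw, with net = c − b. Take no true difference in stress response, 15 per arm and a two-sided 5% t-test. This is a noncentral t with 28 df and noncentrality net × √(15/2).

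| Net (SD) | Falsely block lower | Falsely block higher | Any rejection |
|---|---|---|---|
| −0.25 | 0.4% | 9.7% | 10.1% |
| 0 | 2.5% | 2.5% | 5.0% |
| 0.25 | 9.7% | 0.4% | 10.1% |
| 0.5 | 26.2% | 0.05% | 26.2% |
| 0.75 | 50.9% | about 0% | 50.9% |
| 1.0 | 75.3% | about 0% | 75.3% |

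Every shift here is chosen, not estimated. The table shows only that an unmeasured net shift of moderate size could decide the result in either direction.

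**5. Would drawing before the infiltration solve it?** That sets c = 0 and leaves a net of −b. With the same b at both times, absolute bias falls only if |c − b| > b, that is c > 2b. For b = 0.25, c must exceed 0.5 SD. The moved draw falls sooner after the block, so b could be larger then. With assumed residues of 0.40 SD at the moved draw and 0.25 SD at the later one, c must exceed 0.40 + 0.25 = 0.65 SD. With c = b = 0.25 the later draw has net zero, and the move creates a net of −0.25 SD. After the move, power for a true 1.0 SD suppression would be 75.3% with b = 0 and 50.9% with b = 0.25.

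**6. Baseline order.** Whether the block precedes the baseline draw has no effect on a raw post-op comparison. It would matter for change scores or baseline adjustment, which Sample Size/Statistics does not specify.

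**The case against.** The strongest reply is that nothing in the documents shows a bias of any size. The block arm receives at least as much epinephrine as the control ceiling, the residues may be negligible or may offset each other, and the rejection rates rest on chosen shifts. That is right about magnitude. It does not restore the interpretation: different injection times give no ground to assume cancellation, and as planned the data could not show whether it occurred.

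It may also be said that the draw-time conflict is harmless because both arms carry the same Study Description wording. That stands as far as bias goes. The conflict would become differential only if the time actually used differed by arm. The endpoint is still undefined.

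Finally, this is one of three samples for a secondary aim in a pilot described as likely underpowered, and a 24-hour comparison is already planned. That limits the severity and is accepted.

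A reader might go further and infer that only controls are exposed, so the comparison is tilted toward the block. The block's own 5 mcg/kg rules that out. A reader might also infer that the infiltration comes immediately before the draw. The documents give the order but no interval, and under Study Description the transfer lies between them.

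**Conclusion.** The concern holds in limited form. The immediate post-op contrast mixes injected and endogenous epinephrine, and the planned data cannot separate them. This rests on the protocol's stated injections and sequence alone. The size and net direction of any bias are unknown; the only magnitudes taken from the documents are the loads, 5 mcg/kg against under 5 mcg/kg. The 10% to 75% rejection rates are conditional on assumed net shifts of 0.25 to 1.0 SD and are not estimates for this trial.

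The two draw times contradict each other and must be reconciled, as a matter of endpoint definition and not as a demonstrated source of bias.

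It is tempting to conclude that the post-op draw should simply be moved ahead of the infiltration. Step 5 of the working does not support that as a general improvement, because the gain depends on two unknown quantities. The morphine comparison and the feasibility goals are unaffected, and the 24-hour sample is much less exposed. This is a minor finding.

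**What to change.** Leave the injectates, doses and injection timing as they are, and change the measurement and reporting:

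1. Reconcile Aim 5 and both Study Description paragraphs to one post-op draw time, used in both arms.
2. Take the baseline draw before the block, at the matching point in controls, so that the baseline contains none of the study's injected epinephrine.
3. Record the time and volume of each epinephrine-containing injection and the time of each draw.
4. State that the immediate post-op contrast does not separate injected from endogenous epinephrine and is not by itself evidence of stress suppression. Report the 24-hour comparison alongside, with the number missing by arm.

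The sponsor may weigh taking the post-op sample before wound infiltration. That removes the control-side source, so injected epinephrine could no longer imitate suppression by the block. It also drops closure and transfer from the measured period and leaves any block residue unopposed. It is an option, not the lead fix.

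The cost is protocol wording, a few recorded items and a more limited Aim 5 conclusion. The number of draws stays at three and the blood volume at the 6 mL per patient given under Adverse Event Reporting.

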- Parent or legal guardian willing to participate, and able to understand and sign the provided informed consent

Exclusion Criteria:

- Intubated prior to surgery (patients who have been intubated and subsequently extubated may be included)
- Ongoing septicemia or localized skin infection on the back
- Parent or legal guardian unwilling to participate or unable to understand and sign the provided informed consent
- Known coagulation defect
- Allergy to local anesthetics

Enrollment/Consent process:

The Institutional Review Board will approve informed consent documents prior to commencement of the study. Only those patients who meet the entry criteria will be considered as possible study candidates. A thorough discussion between the parents or legal guardian and the principal investigator, or the study coordinator will occur during the study consent process. No study related procedure will occur prior to obtaining appropriate informed consent.

All participants in this study will be neonates or infants (<12 months old). Patients will be enrolled consecutively as they present to Children's Healthcare of Atlanta. The parents or legal guardian of the neonate will be approached on the day prior to surgery or at presentation to the preoperative evaluation clinic by the investigators or the study coordinator to discuss the goals, benefits and risks of the project. Written informed consent will be obtained following this discussion. For the occasions when parents do not arrive at the hospital until the day of surgery, they will be approached only if there is sufficient time to allow for their full consideration.

Study Description:

Participants in the study will be randomized to the control arm or experimental arm using computer-generated random assignment, which will be prepared at the start of the study and the assignments held in sealed envelopes. Once the participant is enrolled in the study and consent has been obtained the investigator will open the next consecutive sealed envelope which contains the patient's group assignment (experimental or control). If the participant is enrolled in the study and randomized to the experimental procedure an informed consent for treatment must be signed. This is the standard of care for this type of procedure.

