This protocol is designed as a pilot study with limited-efficacy testing. The primary goal is to demonstrate the feasibility of a subsequent randomized clinical trial. In doing so, we will assess the capacity for recruitment and caregiver consent to random assignment. An additional exploratory aim is to evaluate the preliminary efficacy of using a single-shot paravertebral nerve block to decrease perioperative morphine consumption. Because this is a pilot study, the proposed study is likely underpowered to detect a statistically significant result. However, the results (i.e. effect sizes) from this study will be used in sample size and power calculations for a future, larger RCT. We expect that there will be a trend toward lower morphine equivalent consumption in the experimental group that will either reach statistical significance or provide a better estimation of necessary sample size for future funding from extramural sources.

The most similar study available for comparison examined the use of paravertebral nerve catheters in infants undergoing thoracotomy to repair long-gap esophageal atresia. This study was retrospective and several days of morphine consumption were observed. In this retrospective trial of 17 patients, the authors observed a decrease of 36% in morphine consumption per day ($p<0.001$).[6] If such a dramatic decrease in morphine consumption is observed during our prospective study, then it is adequately powered at current sample size 15 in each arm, total 30 patients.

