Descriptive statistics will be calculated for all variables of interest and include means and standard deviations, medians and ranges or counts and percentages, as appropriate. Summary measures will be tabulated overall and by treatment group. Recruitment and consent rates will be calculated with associated 95% confidence intervals. Primary and secondary outcomes will be compared between the two intervention groups. Continuous measures will be compared between groups using two-sample t-tests or Wilcoxon rank-sum tests while categorical variables will be compared using Chi-square tests or Fisher exact tests. Because this is a pilot study, effect sizes will be calculated for all outcomes and will include difference in means, difference in rates, or risk ratios with associated 95% confidence intervals. Analysis will follow the intention to treat principal where all subjects are analyzed based on their randomly assigned treatment whether or not they received the treatment. A p-value less than 0.05 will be considered statistically significant and all statistical testing will be two-sided, unless otherwise noted. Analysis will be conducted using SAS v. 9.4 (Cary, NC) and under direction of the pediatric biostatistics core.

Adverse Event Reporting

Monitoring of Adverse Events (AEs) and Serious Adverse Events (SAEs) is an important aspect of data collection. The study subjects will be reviewed on a case-by-case basis. The principal investigator will determine the seriousness of each adverse event and whether or not the event

was related to the study. Adverse events potentially associated with paravertebral nerve blocks include (from most to least common): block failure, vascular puncture, deep tissue hematoma (SAE), epidural hematoma (SAE), hypotension, lung puncture, pneumothorax, and local anesthetic systemic toxicity (SAE). Hypotension will be defined as a mean arterial pressure less than 30 mm Hg during the first 24 hours after arrival to the CICU.

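### A treatment consent signed only in the block arm, after the envelope is opened, allows one-sided refusals that would dilute the contrast or cause one-sided attrition

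*Combined protocol and SAP*

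**What the plan says.** The Study Description section fixes the order of events. Study consent comes first, and allocation is revealed next: "Once the participant is enrolled in the study and consent has been obtained the investigator will open the next consecutive sealed envelope". A further signature follows for one arm: "If the participant is enrolled in the study and randomized to the experimental procedure an informed consent for treatment must be signed". The stated reason is "This is the standard of care for this type of procedure". No matching step is described for control. The Design section calls the trial non-blinded, with equal allocation: "Subjects will be assigned to nerve block or SOC in a 1:1 ratio".

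The Sample Size/Statistics section sets out what the pilot must deliver. On feasibility, "we will assess the capacity for recruitment and caregiver consent to random assignment", and "Recruitment and consent rates will be calculated with associated 95% confidence intervals". On efficacy, the observed effect sizes are to feed the sample size of a later, larger trial. The analysis is by intention to treat: "all subjects are analyzed based on their randomly assigned treatment whether or not they received the treatment".

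The plan does not say whether a family that declines the treatment consent crosses to standard care, withdraws or is replaced. It gives no expected refusal rate and no allowance for refusals. It does not say which of the two consents the consent rate counts.

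**The concern.** Because the second signature is conditional on assignment to the block, it comes when the family knows the allocation, and it is asked of one arm only. It is mandatory, so without it no block is given. The design therefore contains a decision point after randomisation that exists in one arm and not in the other.

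Two outputs of the pilot are exposed.

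- **The effect size carried forward.** An infant whose family declines but who stays in follow-up is analysed in the block arm without a block, which pulls the difference in morphine equivalents toward zero. If the family withdraws instead, data are lost from one arm only, and intention to treat cannot by itself repair that.
- **The consent rate.** Counted before the envelope is opened, it includes families who accept randomisation but would not accept the block. Refusals seen later do not fully correct it, because control families are never asked.

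**Working it through.** **Inputs from the documents.** 15 per arm, and a 36% reduction in morphine consumption taken from a retrospective study of 17 patients (Sample Size/Statistics). On testing: "A p-value less than 0.05 will be considered statistically significant and all statistical testing will be two-sided, unless otherwise noted".

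**Inputs not in the documents, and so assumed.** The standard deviation (SD), the target power, the number of refusals, and what happens to a refuser.

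**The plan's own figure.** The plan says that 15 per arm is adequate if a 36% reduction is seen. Without an SD this cannot be reproduced. Solving backwards with the two-sample t-test (noncentral t, 28 degrees of freedom, noncentrality d × √(15/2)), 80% power needs a standardised difference d = 1.0598. The SD must then be 0.36 / 1.0598 = 0.34 of the control mean. At an SD of 0.30, 0.35, 0.40 or 0.50 of the control mean, power is 89%, 78%, 66% or 48%. The 80% used below is therefore a reference point, not a claim of the plan.

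**Case A: refusers stay in follow-up under control care.** Let r = k/15 for k refusals, and assume that refusers have on average the control outcome.

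- Intention-to-treat effect = 36% × (1 − r)
- Standardised difference = 1.0598 × (1 − r)
- Inflation of a sample size based on that effect = 1/(1 − r)²
- Number per arm to restore 80% power = 15 × inflation, rounded up

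| Refusals of 15 | r | Effect | d | Power | Inflation | n per arm |
|---|---|---|---|---|---|---|
| 0 | 0 | 36.0% | 1.060 | 80% | 1.00 | 15 |
| 1 | 6.7% | 33.6% | 0.989 | 74% | 1.15 | 18 |
| 2 | 13.3% | 31.2% | 0.918 | 68% | 1.33 | 20 |
| 3 | 20.0% | 28.8% | 0.848 | 61% | 1.56 | 24 |

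Mixing treated and untreated infants also widens the block arm's variance, by r(1 − r) × 0.36² in units of the squared control mean. Allowing for this, power is about 73%, 65% and 57% for 1, 2 and 3 refusals.

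**Case B: refusers withdraw and give no data.** With 15 against 15 − k infants and d unchanged, power is about 78.5%, 76.8% and 74.9% for k = 1, 2 and 3, provided that the loss is unrelated to outcome. The contrast is then not diluted. If the loss is related to outcome, it may be biased.

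**How likely is any refusal?** If each block-arm family declines with probability q, the chance of at least one refusal among 15 is 1 − (1 − q)^15. For q = 2%, 5%, 10% and 20% this is 26%, 54%, 79% and 96%. All four values of q are assumptions.

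**Consent rate, with assumed figures.** Suppose 30 of 40 approached families sign the study consent, and 3 of the 15 assigned to the block then decline. The rate before the envelope is 30/40 = 75%. Subtracting the observed refusals gives 27/40 = 67.5%. If control families would have declined at the same 3/15 = 20%, acceptance of the whole package is 30 × 0.80 / 40 = 60%. The plan as written cannot tell these apart.

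**The case against.** The strongest reply is that refusals may be close to zero. Parents have by then had a full discussion of goals, benefits and risks and have signed the study consent; unwilling parents are excluded; and the second form is presented as ordinary procedural paperwork. This stands. A reader might infer that the step produces refusals, or that each one moves an infant to control care. The documents support neither: they show an opportunity, and they are silent on what follows a refusal.

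Second, the trial is unblinded and no signature is binding, so a parent in either arm could still change their mind after the envelope is opened. This also stands. Signing earlier removes one structural prompt to refuse, not every refusal.

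Third, the pilot calls itself likely underpowered, so a loss of power from an 80% that it never claims carries little weight. That is fair for the significance test. It does not cover the effect size, which the plan says it will use to size the next trial.

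Fourth, consent to randomisation is what the first signature records, and a later refusal is a matter of adherence that a pilot may usefully observe. If the later trial kept the same sequence, an effect that includes refusals would also be relevant to it. This stands in part. The plan neither says that it will count such refusals nor reports them by arm, and 15 families estimate the rate poorly: even 0 refusals of 15 leaves a two-sided 95% upper limit of 1 − 0.025^(1/15) = 22%.

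The procedural-consent rationale explains why a second form is needed. It does not explain why the form must follow allocation.

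**Conclusion.** The point holds as a structural weakness. The plan puts a decision point after allocation in the block arm only, and no other section removes it. Its size is unknown. The 33.6%, 31.2% and 28.8% effects, and the matching power and inflation figures, are illustrations. They rest on an assumed 80% starting power, an assumed number of refusals, and refusers being followed under control care with control-like outcomes. If refusers withdrew, the problem would be one-sided missing data.

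A reader might also infer that intention to treat is at fault. It is not: it is the proper analysis and guards against selection bias when refusers remain in follow-up. It simply does not prevent dilution or missing data.

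The stake lies mainly in the two outputs that the pilot exists to provide, the consent rate and the effect size for the next trial. This is a cheap improvement, not a flaw that invalidates the design.

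**What to change.** Revise the Study Description so that the nerve-block treatment consent is discussed with every family and signed conditionally before the next envelope is opened. Count families who decline it as not consenting to randomisation, and say so where the Sample Size/Statistics section defines the consent rate. Add that any later change of mind will be reported by arm, with the infant kept in follow-up and analysed as randomised.

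The cost is a change in the order of paperwork, revised wording for the Institutional Review Board, and one extra form for families later assigned to control. That form might slightly lower the measured consent rate, but the rate would then describe families willing to accept either assignment.
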